3.1.5. Pharmacokinetic/Immunogenicity Assessments

Sparse plasma/serum PK/immunogenicity sampling will be collected for avelumab and anti-drug antibodies (ADA). Sampling will only be done in patients randomized to Arm A. Refer to the [Schedule of Activities](#) table and [Sections 7.3](#) and [7.4](#) for additional details of the PK and immunogenicity collections.

3.1.6. Biomarker Assessments

Mandatory baseline (recent) tumor tissue, as well as archival tumor tissue, if available, will be collected from all patients to support investigation and, as appropriate, clinical validation of biomarkers that may predict response to treatment. End of Treatment tumor tissue from a *de novo* biopsy should also be obtained unless clinically contraindicated to support an investigation of mechanisms of resistance. Banked blood biospecimen will be collected from all patients at baseline, on treatment and at End of Treatment/Withdrawal to support exploratory investigation of possible markers predictive of clinical benefit, pharmacodynamic markers and/or markers of intrinsic or acquired resistance.

Biomarker assessments are described in the [Schedule of Activities](#) table and in [Section 7.5](#) and [Section 7.6](#).

4. PATIENT SELECTION

This study can fulfill its objectives only if appropriate patients are enrolled. The following eligibility criteria are designed to select patients for whom participation in the study is considered appropriate. All relevant medical and non-medical conditions should be taken into consideration when deciding whether a particular patient is suitable for this protocol.

4.1. Inclusion Criteria

Patient eligibility should be reviewed and documented by an appropriate member of the investigator's study team before patients are included in the study.

Patients must meet all of the following inclusion criteria to be eligible for enrollment into the study:

1. Diagnosis:
 - a. Histologically confirmed, unresectable locally advanced or metastatic transitional cell carcinoma of the urothelium.
 - b. Documented Stage IV disease (per American Joint Committee on Cancer/International Union for Cancer Control Tumor Node Metastasis (TNM) system, 7th edition)⁶⁵ at the start of first-line chemotherapy.
 - c. Measurable disease prior to the start of first-line chemotherapy by RECIST v1.1.
2. Prior first-line chemotherapy must have consisted of at least 4 cycles and no more than 6 cycles of gemcitabine + cisplatin and/or gemcitabine + carboplatin. No other chemotherapy regimens are allowed in this study.
 - a. The last dose of first-line chemotherapy must have been received no less than 4 weeks, and no more than 10 weeks, prior to randomization in the present study.
3. Patients without progressive disease as per RECIST v1.1 guidelines (ie, with an ongoing CR, PR, or SD) following completion of 4 to 6 cycles of first-line chemotherapy.
 - a. Eligibility based on this criterion will be determined by investigator review of pre-chemotherapy and post-chemotherapy radiological assessments (CT/MRI scans); see Study Overview, [Section 3.1](#).
4. Provision of a recent formalin-fixed, paraffin-embedded (FFPE) tumor tissue block (or subsection thereof) from the most recent primary or metastatic tumor biopsy or resection obtained prior to treatment with first line chemotherapy but within 24 months prior to randomization, with no intervening systemic anti-cancer therapy. If a FFPE tissue block cannot be provided, 15 freshly cut unstained slides (10 minimum) will be acceptable.

If a suitable tissue sample is not otherwise available, then a *de novo* biopsy (core needle or excisional) must have been obtained for research purposes prior to randomization in this study.

Note: tumor tissue from cytologic sampling (eg, fine needle aspiration, including FFPE cell pellet material) or bone metastases are not acceptable and should not be submitted.
5. Evidence of a signed and dated informed consent document indicating that the patient (or a legally acceptable representative, as allowed by local guideline/practice) has been informed of all pertinent aspects of the study.

6. Patients who are willing and able to comply with scheduled visits, treatment plans, laboratory tests, and other study procedures.
7. Age ≥ 18 years (≥ 20 years in Japan).
8. Estimated life expectancy of at least 3 months.
9. Eastern Cooperative Oncology Group (ECOG) performance status (PS) 0 or 1 ([Appendix 1](#)).
10. Adequate bone marrow function, including:
 - a. Absolute neutrophil count (ANC) $\geq 1,500/\text{mm}^3$ or $\geq 1.5 \times 10^9/\text{L}$;
 - b. Platelets $\geq 100,000/\text{mm}^3$ or $\geq 100 \times 10^9/\text{L}$;
 - c. Hemoglobin ≥ 9 g/dL (may have been transfused).
11. Adequate renal function, defined as estimated creatinine clearance ≥ 30 mL/min as calculated using the Cockcroft-Gault equation ([Appendix 4](#)) or by 24-hour urine collection for creatinine clearance or according to the local institutional standard method.
12. Adequate liver function, including:
 - a. Total serum bilirubin ≤ 1.5 x upper limit of normal (ULN);
 - b. Aspartate aminotransferase (AST) and alanine aminotransferase (ALT) ≤ 2.5 x ULN, or, for patients with documented metastatic disease to the liver, AST and ALT levels $\leq 5 \times$ ULN.
13. Serum pregnancy test (for females of childbearing potential) negative at screening.
14. Female patients of childbearing potential and at risk for pregnancy must agree to use a highly effective method of contraception ([Section 4.3.1](#)) throughout the study and for at least 30 days after the last dose of assigned treatment.

4.2. Exclusion Criteria

Patients with any of the following characteristics/conditions will not be included in the study:

1. Patients whose disease progressed by RECIST v1.1 on or after first-line chemotherapy for urothelial cancer.
2. Prior adjuvant or neoadjuvant systemic therapy within 12 months of randomization.

3. Prior immunotherapy with IL-2, IFN- α , or an anti-PD-1, anti-PD-L1, anti-PD-L2, anti-CD137, or CTLA-4 antibody (including ipilimumab), or any other antibody or drug specifically targeting T-cell co-stimulation or immune checkpoint pathways.
4. Major surgery ≤ 4 weeks or major radiation therapy ≤ 2 weeks prior to randomization. Prior palliative radiotherapy is permitted, provided it has been completed at least 48 hours prior to patient randomization.
5. Patients with known symptomatic central nervous system (CNS) metastases requiring steroids. Patients with previously diagnosed CNS metastases are eligible if they have completed their treatment and have recovered from the acute effects of radiation therapy or surgery prior to randomization, have discontinued corticosteroid treatment for these metastases for at least 4 weeks, and are neurologically stable.
6. Persisting toxicity related to prior therapy NCI CTCAE v4.0 Grade >1 ; however, alopecia, sensory neuropathy Grade ≤ 2 is acceptable, or other Grade ≤ 2 adverse events not constituting a safety risk based on the investigator's judgment are acceptable.
7. Diagnosis of any other malignancy within 5 years prior to randomization, except for adequately treated basal cell or squamous cell skin cancer, or carcinoma in situ of the breast or of the cervix, low-grade (Gleason ≤ 6) prostate cancer on surveillance without any plans for treatment intervention (eg, surgery, radiation, or castration), or prostate cancer that has been adequately treated with prostatectomy or radiotherapy and currently with no evidence of disease or symptoms.
8. Participation in other studies involving investigational drug(s) within 4 weeks prior to randomization. Observational studies are permitted.
9. Active autoimmune disease that might deteriorate when receiving an immunostimulatory agent. Patients with diabetes type I, vitiligo, psoriasis, or hypo- or hyperthyroid disease not requiring immunosuppressive treatment are eligible.
10. Clinically significant (ie, active) cardiovascular disease: cerebral vascular accident/stroke (<6 months prior to enrollment), myocardial infarction (<6 months prior to enrollment), unstable angina, congestive heart failure (\geq New York Heart Association Classification Class II), or serious cardiac arrhythmia requiring medication.
11. Active infection requiring systemic therapy.
12. Known severe hypersensitivity reactions to monoclonal antibodies (Grade ≥ 3), any history of anaphylaxis, or uncontrolled asthma (ie, 3 or more features of asthma symptom control per the Global Initiative for Asthma 2015).⁶⁶

13. Known prior or suspected hypersensitivity to study drugs or any component in their formulations.
14. Current or prior use of immunosuppressive medication within 7 days prior to randomization, EXCEPT the following:
 - a. Intranasal, inhaled, topical steroids, or local steroid injections (eg, intra-articular injection);
 - b. Systemic corticosteroids at physiologic doses ≤ 10 mg/day of prednisone or equivalent;
 - c. Steroids as premedication for hypersensitivity reactions (eg, CT scan premedication).
15. Diagnosis of prior immunodeficiency or organ transplant requiring immunosuppressive therapy.
16. Positive test for human immunodeficiency virus (HIV) infection or known acquired immunodeficiency syndrome (AIDS).
17. Hepatitis B virus (HBV) or hepatitis C virus (HCV) infection at screening (positive HBV surface antigen or HCV RNA if anti-HCV antibody screening test positive).
18. Vaccination within 4 weeks of the first dose of study treatment and while on trial is prohibited except for administration of inactivate vaccines (for example, inactivated influenza vaccines).
19. Patients who are investigational site staff members directly involved in the conduct of the study and their family members, site staff members otherwise supervised by the investigator, or patients who are Pfizer employees directly involved in the conduct of the study.
20. Pregnant female patients; breastfeeding female patients; and female patients of childbearing potential who are unwilling or unable to use a highly effective method of contraception as outlined in the protocol for the duration of the study and for at least 30 days after the last dose of investigational product.
21. Other severe acute or chronic medical conditions including but not limited to colitis, inflammatory bowel disease, pneumonitis, and pulmonary fibrosis; psychiatric condition including recent (within the past year) or active suicidal ideation or behavior; or laboratory abnormality that may increase the risk associated with study participation or study treatment administration or may interfere with the interpretation of study results and, in the judgment of the investigator, would make the patient inappropriate for entry into this study.

4.3. Lifestyle Guidelines

4.3.1. Contraception

Contraception use and pregnancy test will be evaluated in all patients at screening prior to randomization. However, following assignment to treatment only patients assigned to Arm A (avelumab plus BSC) will be required to remain on contraception as described below.

In Arm A of this study, female patients who are of childbearing potential will receive avelumab for which the teratogenic risk is currently unknown.

All female patients of childbearing potential who are, in the opinion of the Investigator, sexually active and at risk for pregnancy must agree to use a highly effective contraception method, preferably with low user dependency, during treatment and for at least 30 days after the last dose. The investigator or his or her designee, in consultation with the patient, will select an appropriate method of contraception for the individual patient from the list of permitted contraception methods (see below), and instruct the patient in its consistent and correct use.

Patients need to affirm that they meet the criteria for the correct use of the selected method of contraception. At time points indicated in the [Schedule of Activities](#), the investigator or his or her designee will discuss with the patient the need to use the selected contraception method consistently and correctly and document such conversation, and the patient's affirmation, in the patient's chart. In addition, the investigator or his or her designee will instruct the patient to call immediately if the selected contraception methods are discontinued, or if pregnancy is known or suspected in the patient or to the male patient's partner.

Contraception Methods

Highly Effective Methods of Contraception That Have Low User Dependence include the following:

1. Implantable progestogen- only hormonal contraception associated with the inhibition of ovulation.
2. Intrauterine device (IUD).
3. Intra-uterine hormone-releasing system (IUS).
4. Vasectomized partner.
 - Vasectomized partner is a highly effective contraceptive method provided that the male partner is the sole sexual partner of the female of child-bearing potential and the absence of sperm has been confirmed. If not, an additional highly effective method of contraception should be used.
5. Bilateral tubal occlusion.

Highly Effective Methods of Contraception That Are User Dependent include the following:

1. Combined (estrogen- and progestogen-containing) hormonal contraception associated with inhibition of ovulation:
 - Oral;
 - Intravaginal;
 - Transdermal;
 - Injectable.
2. Progestogen-only hormone contraception associated with inhibition of ovulation:
 - Oral;
 - Injectable.
3. Sexual abstinence.
 - Sexual abstinence is considered a highly effective method only if defined as refraining from heterosexual intercourse during the entire period of risk associated with the study intervention. The reliability of sexual abstinence needs to be evaluated in relation to the duration of the trial and the preferred and usual lifestyle of the participant.

Female patients of nonchildbearing potential must meet at least 1 of the following criteria:

- Have undergone a documented hysterectomy and/or bilateral oophorectomy;
- Have medically confirmed ovarian failure; or
- Achieved postmenopausal status, defined as 60 years or older or no cessation of regular menses for at least 12 consecutive months with no alternative pathological or physiological cause. Status may be confirmed by having a serum follicle-stimulating hormone (FSH) level test.

All other female patients (including females with tubal ligations) will be considered to be of childbearing potential.

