| 9. | Serum/Urine Pregnancy Test: For female patients of childbearing potential, a serum or urine pregnancy test, with sensitivity of at least 25 mIU/mL, will be routinely repeated prior to each avelumab dose during the active treatment period, at the End of Treatment/Withdrawal visit, and additionally whenever one menstrual cycle is missed or when potential pregnancy is otherwise suspected. Additional pregnancy tests may also be undertaken if requested by Institutional Review Board (IRB)/Ethics Committees (ECs) or if required by local regulations. Results of the pregnancy test should be available prior to each dosing. See Section 7.1.1 . |
| 10. | 12-Lead Electrocardiogram (ECG): To be performed as clinically indicated. Clinically significant new findings seen on follow-up ECGs should be recorded as adverse events. |
| 11. | Tumor Assessments: Tumor assessments will be performed at a frequency as per local standard of care and when progression is suspected. The tumor assessment data will no longer be entered into the CRF and radiologic images will no longer be submitted for central imaging review. |

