7.1.1. Pregnancy Testing

For female patients of childbearing potential, a serum pregnancy test, with sensitivity of at least 25 mIU/mL, will be performed on 2 occasions prior to starting study treatment: once at the start of screening, and once at the Cycle 1 Day 1 visit for Arm A patients immediately before the administration of study treatment. Following a negative pregnancy test result at screening, appropriate contraception must be commenced and another negative pregnancy test result will then be required at the Cycle 1 Day 1 visit before the patient may receive avelumab study treatment. For patients receiving avelumab study treatment, serum or urine pregnancy tests will also be routinely repeated as described in the [Schedule of Activities](#) tables and additionally whenever 1 menstrual cycle is missed or when potential pregnancy is otherwise suspected. In the case of a positive human chorionic gonadotropin (hCG) test, the patient will be withdrawn from treatment but may remain in the study.

Additional pregnancy tests may also be undertaken if requested by Institutional Review Board/Ethics Committees (IRB/ECs) or if required by local regulations.

As per Protocol Amendment 6, following the final OS update, negative pregnancy test results need not be recorded in the CRF.

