8. Current or prior use of immunosuppressive medication within 7 days prior to avelumab treatment (Cycle CR1 Day 1), EXCEPT the following:
 - a. Intranasal, inhaled, topical steroids, or local steroid injections (eg, intra-articular injection);

- b. Systemic corticosteroids at physiologic doses ≤ 10 mg/day of prednisone or equivalent;
 - c. Steroids as premedication for hypersensitivity reactions (eg, CT scan premedication).
9. Diagnosis of prior immunodeficiency or organ transplant requiring immunosuppressive therapy.
10. Vaccination within 4 weeks of the first dose of avelumab treatment and while on trial is prohibited except for administration of inactivate vaccines (for example, inactivated influenza vaccines).
11. Breastfeeding female patients and female patients of childbearing potential who are unwilling or unable to use a highly effective method of contraception as outlined in the protocol [Section 4.3.1](#) for the duration of the study and for at least 30 days after the last dose of investigational product.
12. Other severe acute or chronic medical conditions including but not limited to HIV, HBV, or HCV infection, colitis, inflammatory bowel disease, pneumonitis, and pulmonary fibrosis; psychiatric condition including recent (within the past year) or active suicidal ideation or behavior; or laboratory abnormality that may increase the risk associated with study participation or study treatment administration or may interfere with the interpretation of study results and, in the judgment of the investigator, would make the patient inappropriate for entry into this study.

GENERAL TREATMENT/STUDY PLAN

Patients who crossover from BSC alone to avelumab plus BSC will receive avelumab at 10 mg/kg on Day 1 and Day 15 of each 4-week treatment cycle after all procedures/assessments have been completed as described in the [SOA](#) table.

With the exception of the detailed SOA provided below, all study treatments, concomitant medication restrictions, AE reporting, etc, described for patients randomized to Arm A in [Section 5](#) through [Section 7.1](#) and [Section 8](#) of the study protocol will be followed for patients who crossover from Arm B to avelumab plus BSC.

SCHEDULE OF ACTIVITIES FOR PATIENTS WHO CROSSOVER FROM ARM B TO AVELUMAB PLUS BSC

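### A stray word in Protocol Section 4.3.1 inverts the postmenopausal definition for women under 60

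*Protocol*

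**What the plan says.** Section 4.3.1 (Contraception) ends with criteria for women of nonchildbearing potential, and meeting any one of them suffices. The first is documented hysterectomy and/or bilateral oophorectomy, and the second is medically confirmed ovarian failure. The third is: "Achieved postmenopausal status, defined as 60 years or older or no cessation of regular menses for at least 12 consecutive months", continued by "with no alternative pathological or physiological cause", with an FSH level offered as confirmation. Everyone else is covered by a residual rule: "All other female patients (including females with tubal ligations) will be considered to be of childbearing potential".

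The same section explains why the classification matters: women of childbearing potential in Arm A receive "avelumab for which the teratogenic risk is currently unknown".

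The classification is then used throughout the protocol:

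- **Section 4.1, inclusion criterion 13:** the negative screening pregnancy test is asked only of females of childbearing potential.
- **Section 4.1, inclusion criterion 14:** "Female patients of childbearing potential and at risk for pregnancy must agree to use a highly effective method of contraception".
- **Section 7.1.1:** for the same women, pregnancy tests are repeated on avelumab as scheduled and "additionally whenever 1 menstrual cycle is missed or when potential pregnancy is otherwise suspected".
- **Amendment 6 Schedule of Activities, footnote 9:** for the same women, the test "will be routinely repeated prior to each avelumab dose during the active treatment period". Footnote 6, the contraception check, refers back to Section 4.3.1.
- **Supplement 1 (crossover from Arm B):** inclusion criterion 9 asks for a negative test only from females of childbearing potential. Exclusion criterion 11 bars "female patients of childbearing potential who are unwilling or unable to use a highly effective method of contraception" and cites Section 4.3.1.

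**The concern.** The definition says the opposite of what it must mean. Menopause is established by menses having stopped for a year without another explanation, whereas the clause asks that they have not stopped. Because one criterion is enough and all remaining women go to the other class, reversing this criterion changes the classification in both directions for women under 60 who meet neither of the other two.

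The more serious direction is the exemption. A menstruating woman under 60 would fall outside the contraception and repeat pregnancy-test requirements while receiving a drug of unknown teratogenic risk. In the other direction, a woman under 60 who is truly postmenopausal would be given pregnancy tests, and possibly a contraception obligation, that she does not need.

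This is operative text in the current protocol. It still applies to patients on avelumab under the Amendment 6 schedule and to Arm B patients who cross over.

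**Working it through.** The plan gives no figure to reproduce. The check is a reading of the clause against the rest of the protocol, with one line of arithmetic.

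**Step 1: literal classification.** Take a woman under 60 with no hysterectomy, no bilateral oophorectomy and no confirmed ovarian failure, so that only the third criterion can apply.

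| Menstrual history | Clause as written | Clause with *no* deleted | Correct class |
|---|---|---|---|
| Regular menses over the past 12 months | Criterion met: not of childbearing potential | Criterion not met: childbearing potential | Childbearing potential |
| Menses stopped 12 or more months ago, no other cause | Criterion not met: childbearing potential, by the residual rule | Criterion met: not of childbearing potential | Not of childbearing potential |

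As written, both rows are wrong. With the one word removed, both are right. Women aged 60 or older qualify through the age limb and are unaffected either way.

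**Step 2: is the intended meaning in doubt?** Three things in the protocol make sense only if the clause is about menses that have stopped:

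- The criterion is headed as achieved postmenopausal status.
- The qualifier "with no alternative pathological or physiological cause" and the FSH confirmation presuppose an absence of menses that needs explaining.
- The extra test after a missed cycle, in Section 7.1.1 and the Schedule of Activities footnotes, treats menstruating women as able to conceive.

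**Step 3: is it corrected elsewhere?** No other section defines postmenopausal status or nonchildbearing potential. Supplement 1 points back to Section 4.3.1, so crossover patients inherit the clause.

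**Step 4: what else guards against pregnancy?** In the main study, exclusion criterion 20 (Section 4.2) bars pregnant patients outright, whatever their classification. The crossover exclusions contain no such bar. Criterion 11 names breastfeeding patients and those of childbearing potential who will not or cannot use contraception, and inclusion criterion 9 limits the negative test to females of childbearing potential. In the crossover criteria, pregnancy screening therefore rests on the misdefined term. Pregnancy remains a listed reason for stopping treatment (Section 6.5).

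**Step 5: size for one woman.** Testing precedes each dose and dosing is every 2 weeks, so 52 / 2 = 26 scheduled tests a year would not be required for a woman wrongly exempted. The documents do not give the number of such women.

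**The case against.** There is no defence of the wording itself. The case on the other side concerns how far the consequences reach.

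- **The literal reading contradicts itself.** A clinician would be unlikely to class a regularly menstruating woman as postmenopausal on a clause that also asks for no alternative cause and offers FSH confirmation. This stands, and it is the main reason to expect little or no harm.
- **Screening backstop.** Section 4.3.1 opens by saying that contraception use and pregnancy testing are evaluated in all patients at screening. This helps at entry, but inclusion criterion 13 restricts the required test to females of childbearing potential, and the opening line does not cover the repeat tests on treatment.
- **The second direction is softer.** The contraception duty in Section 4.3.1 and inclusion criterion 14 also requires that the woman be at risk for pregnancy, which an investigator would not say of a truly postmenopausal woman. For her, the practical burden would mostly be unnecessary tests. This largely stands, although exclusion criterion 20 and crossover exclusion criterion 11 omit the qualifier.
- **Few women reach the clause.** In the avelumab urothelial cohorts cited in Section 1.2.3.2, the median age was 68. If this trial is similar, which is an assumption, most women qualify by age alone. Enrollment is also complete: Section 9.6 required all initially planned patients to be randomized before the interim analysis, which has taken place. Crossover closes 60 days after the final OS update or approval of Amendment 6, whichever is later. This stands.
- **The 26 tests are hypothetical.** They describe one woman under a reading that sites probably would not adopt, and ethics committees or local regulations may require extra tests in any case. The figure is a per-woman illustration and does not estimate impact.

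**Conclusion.** The concern holds as a minor, wrong-as-written drafting error in a safety definition. The literal text misclassifies women under 60 in both directions, nothing else in the protocol overrides it, and it controls pregnancy screening and monitoring on a drug of unknown teratogenic risk. The crossover criteria depend on it most, because they contain no outright exclusion of pregnant patients.

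The expected practical effect is small. That judgement assumes that sites apply the evident intent and that few women under 60 depend on this criterion. The documents do not give the number, and they do not show when the word entered the text, so it cannot be said whether any patient was classified under it. There is no effect on overall survival, event counts, alpha, power or any planned analysis.

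**What to change.** In Section 4.3.1, delete *no* before *cessation*. The under-60 limb then requires that regular menses have ceased for at least 12 consecutive months, and the rest of the sentence ("with no alternative pathological or physiological cause") stays as it is. Supplement 1 and the Amendment 6 schedule need no separate edit to the definition, because their contraception provisions refer to this section.

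Notify sites by administrative change letter, a route the sponsor has already used in this study for clarifications such as the timing of vital signs. The cost is one word and one letter, with no change to the statistical design, the SAP or data collection.
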